1.0 Introduction

1.1 Study Conduct

This study will be conducted in compliance with the protocol approved by the Institutional Review Board, and according to Good Clinical Practice standards. No deviation from the protocol will be implemented without the prior review and approval of the IRB except where it may be necessary to eliminate an immediate hazard to a research subject. In such case, the deviation will be reported to the IRB according to its policies and procedures.

1.2 Background

Over the past 5 years, data has emerged from numerous countries supporting the safety and efficacy of prostatic artery embolization (PAE) for the treatment of lower urinary tract symptoms (LUTS) in the setting of benign prostatic hyperplasia (BPH) (1). In response, the Food and Drug Administration (FDA) recently granted a de novo classification to Merit Medical Systems to expand the indications for Embosphere Microspheres to include PAE for the treatment of BPH. Moreover, it has given 510(k) clearance for Embozene Microspheres.

LC Bead LUMI is a spherical polyvinyl alcohol embolic particle that has become available for clinical use over the last two years. It is unique among embolic particles in that it is innately radiopaque. It is a reengineered iteration of LC Bead that now includes iodine moieties to provide radiopacity (2). A disadvantage of the new molecular structure is that it has a shorter suspension time and less compressibility (2). These factors can lead to clumping and sub-optimal proximal embolization.

While PAE is clinically effective in as many as 75% of patients at 2-year follow-up (3), there is still uncertainty as to the reasons for failure. Additionally, although they are rare, several major complications have occurred as a result of non-target embolization during PAE (1). Because LUMI is inherently radiopaque, its distribution can be imaged on post-embolization conventional or cone beam computed tomography (CT). If used for PAE, these scans could provide information about completeness of prostate embolization as well as the presence of non-target embolization, leading to improved embolization techniques and patient selection. Before these avenues can be investigated, it must be determined if PAE can be performed effectively and safely with LC Bead LUMI.

1.3 Medical Device

1.3.1 Name of Investigational Device

LC Bead LUMI (M0 or M1 bead sizes are acceptable for use in this trial)

1.3.2 Intended Use of the Investigational Device

LC Bead LUMI will be used for prostatic artery embolization in patients with BPH.

1.3.3 Description of the Investigational Device

LC Bead LUMI is a spherical polyvinyl alcohol embolic particle that incorporates radiopaque moieties (2). Once a catheter has been fluoroscopically guided into the target vessel, the beads are then injected, causing obstruction at the arteriole level

until the desired degree of embolization has occurred. We do not anticipate any changes in our use of the microspheres during the study.

1.4 Preclinical Data

LC Bead LUMI has undergone in vitro testing to evaluate its duration of suspension in solution, density in solution and deliverability through a catheter, as well as its degree of opacity on fluoroscopy and CT (2). In vivo testing in a rabbit VX2 tumor model demonstrated high visibility of the particles after embolization on fluoroscopy and cone beam CT (2). Similar in vivo testing was done in a swine model also demonstrating visibility under fluoroscopy and CT (4). Further swine liver model testing revealed that LC Bead LUMI is effective for embolization resulting in predictable ischemia/necrosis and excellent long-term biocompatibility (2).

1.5 Clinical Data to Date

There is no published data available for PAE with LC Bead LUMI. There is a case series reporting safe, successful use of LC Bead LUMI for the treatment of liver cancer in humans (5). There is also data supporting the safe and effective use of a closely related embolic (*Bead Block*-also a spherical polyvinyl alcohol embolic particle manufactured by BTG) for PAE (6).

1.6 Similar Approved Devices

To date there are 2 embolic devices that are approved for the indication of PAE, Embospheres and Embozene Microspheres. Embospheres was approved with a de novo classification request (see https://www.accessdata.fda.gov/cdrh_docs/reviews/DEN160040.pdf). Embozene Microspheres received 510(k) clearance (see https://www.accessdata.fda.gov/cdrh_docs/pdf18/K180102.pdf).

1.6.1 Safety and Efficacy of Embospheres

Based on a phase 3 multicenter clinical trial, the procedure using Embospheres was efficacious as 100% of subjects treated with PAE achieved a decrease of 3 or greater in IPSS. There were a total of 123 adverse events in the PAE group, of which 86% were classified as mild. Serious adverse events in PAE patients were limited to urinary retention, sepsis, fever, UTI, rigors, and nausea in one patient each. A second study has included 2 patients at the time of the FDA filing. These 2 patients saw success in IPSS scores with no adverse events reported. A third trial also saw improvement in 4 patients at the time of FDA filing without any occurrence of reported adverse events.

A review of retrospective patient information for 286 patients also demonstrated efficacy of PAE with 97% of subjects demonstrating a reduction of IPSS of 3 or greater at 9-16 months. A total of 85% of total patients experience an adverse event with the majority being post-PAE syndrome, which is mild pain in the perineum, retropubic area, and/or urthra; fever; nausea (74.1%). Serious adverse events occurred in 1%.

1.6.2 Safety and Efficacy of Embozene Microspheres

Embozene is similar in size and material composition to Embospheres. This device also has similar indications for use. While there are some slight differences in the

two products, they do not affect the overall safety and efficacy of Embozene Microspheres.

Safety and efficacy was evaluated for Embozene Microspheres in a total of 38 patients that underwent PAE for the treatment of BPH in a prospective, single center study. Of these patients, 81.8% saw a reduction of at least 3 points of IPSS within 12 months. A total of 47% of patients demonstrated symptomatic improvement over baseline at 12 months. There was also evidence of a reduction in the size of the prostate following the PAE procedure. Overall, the study revealed a 100% success rate without incidence of non-targeted embolization. In regards to safety, the study revealed that PAE was safe as there was only an incidence of adverse events in 39.5% of patients, with no serious adverse events reported. The study did not report any incidence of post-PAE syndrome.

2.0 Study Objectives

The purpose of this pilot study is to determine preliminary estimates of the parameters related to the distribution of the study endpoints including: IPSS and QoL score changes, Qmax changes, PVR changes, percent prostate infarction and presence of non-target embolization.

3.0 Study Design

3.1 General Design

This will be an open label pilot study with a small population undergoing an intervention to determine initial safety and potential for efficacy as measured by improvement of LUTS and decrease in prostate size

3.2 Primary Study Endpoint

Reduction in IPSS at 6 months

3.3 Secondary Study Endpoints

1. Improvement of QoL score at 6 months
2. Improvement of uroflowmetry (Qmax, PVR) at 6 months
3. Reduction of prostate volume at 6 months
4. Percentage of prostate infarcted at 6 months
5. Incidence of non-target embolization at 6 months
6. Incidence of minor complications at 6 months
7. Improvement in IIEF at 6 months

3.4 Primary Safety Endpoints

1. Incidence and classification of major device related complications using Clavien-Dindo classification system at 6 months

3.5 Secondary Safety Endpoints

1. Incidence and classification of minor device related complications using Clavien-Dindo classification system at 6 months

4.0 Subject Selection and Withdrawal

4.1 General Characteristics of the Proposed Subject Population

Study subjects will be men with moderate severe LUTS refractory to medication with measured prostate gland size >50 grams.

4.2 Anticipated Number of Research Subjects

Enrollment into the investigation will be defined as providing informed consent for study participation per IRB policies.

Twenty subjects will be enrolled and all are anticipated to complete the study.

4.3 Inclusion Criteria

1. Male
2. Age > 40
3. Prostate gland >50 grams as measured by pre-procedural CT
4. Have previously taken BPH medication for 6 months without desired improvement of LUTS or has started medication and stopped due to unwanted side effects
5. Moderate to severe LUTS as defined by IPSS score >18
6. Peak urine flow rate (Qmax) <12 ml/sec
7. Capable of giving informed consent
8. Life expectancy greater than 1 year

4.4 Exclusion Criteria

1. Severe vascular disease
2. Uncontrolled diabetes mellitus
3. Immunosuppression
4. Neurogenic bladder and/or sphincter abnormalities secondary to Parkinson's disease, multiple sclerosis, cerebral vascular accident, diabetes, etc.
5. Complete urinary retention
6. Impaired kidney function (serum creatinine level > 1.8 mg/dl or a glomerular filtration rate < 60 as approximated using serum creatinine levels) unless anuric and on dialysis.
7. Confirmed or suspected bladder cancer
8. Urethral strictures, bladder neck contracture, or other potentially confounding bladder pathology
9. Ongoing urogenital infection
10. Previous pelvic radiation or radical pelvic surgery
11. Confirmed or suspected malignancy of the prostate based on DRE, TRUS or PSA (> 10 ng/ml or > 4.0 ng/ml and < 10 ng/ml with free PSA < 25% of total PSA without a negative biopsy).
12. Uncorrectable coagulopathy including INR > 1.5 or platelets < 50,000
13. Contrast hypersensitivity refractory to standard medications (antihistamines, steroids)

4.5 Subject Recruitment and Screening

Subjects will be recruited from the urology and vascular & interventional clinics at the University of North Carolina Hospital as well as at outlying clinics staffed by UNC Urology. A second site, Vascular Institute of Virginia, will also recruit patients from interventional radiology and urology clinics in the Northern Virginia Area.

4.6 Early Withdrawal of Subjects

4.6.1 Criteria for Removal from Study

Subjects will be withdrawn from the study if a major complication occurs that prevents completion of PAE or the ability to complete the follow up visits. Patients may also withdraw at any point at their discretion. Data will be included with an intent to treat analysis. Reasons for study withdrawal will be recorded.

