4.6.2 Follow-up for Withdrawn Subjects

If a subject withdraws from the study, any recorded data will still be included in the analysis. Subjects will only be replaced if they withdrew prior to undergoing PAE.

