8.3 Subject Population(s) for Analysis

All subjects' data will be included for analysis even if follow up data is incomplete. Every attempt will be made to ensure that there is as little missing data as possible including reminder phone calls and follow-up phone calls if a subject misses a visit.

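### A major complication that stops the PAE removes the man from the study, so his 6-month efficacy data are lost despite the stated intent-to-treat analysis

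*Combined protocol and SAP*

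**What the plan says.** Section 4.6.1 sets the removal rule, which has two limbs. The first reads: "Subjects will be withdrawn from the study if a major complication occurs that prevents completion of PAE". It covers men whose procedure was cut short, whether or not they can attend later. The second limb, in the same sentence, covers men whom a major complication leaves unable to attend. The same paragraph adds: "Data will be included with an intent to treat analysis".

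Section 4.6.2 says what happens to the data: "If a subject withdraws from the study, any recorded data will still be included in the analysis". On replacement it says: "Subjects will only be replaced if they withdrew prior to undergoing PAE". No section schedules efficacy visits after withdrawal.

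The primary endpoint (3.2) is "Reduction in IPSS at 6 months". The primary safety endpoint (3.4) is "Incidence and classification of major device related complications using Clavien-Dindo classification system at 6 months". Section 8.3 says that all subjects' "data will be included for analysis even if follow up data is incomplete", and relies on reminder and follow-up telephone calls to limit missing data. Section 8.2 lists means, standard deviations, fractions and percent change from baseline to a final value that it does not define. Neither 8.2 nor 8.3 names a denominator for the success rates or a rule for a missing 6-month IPSS.

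**The concern.** Under the first limb of 4.6.1 the protocol itself creates the missing data, and does so because the procedure went badly. A man withdrawn at the procedure cannot contribute to any change from baseline. Keeping his recorded data does not help, because the only IPSS recorded is the baseline one. The intent-to-treat statement therefore has nothing to work on for the primary endpoint.

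The pilot exists to supply endpoint estimates (2.0) and sample-size data for a larger trial (8.1). If the men with stopped procedures drop out of the efficacy figures, those estimates lean in the device's favour.

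He also misses the 3-month CT (6.5), the only scheduled post-procedure imaging for non-target embolization, prostate volume and percent infarction. Non-target embolization is a named secondary endpoint (3.3). Beads may already have been injected on one side, since 5.1 describes the two sides being embolized in turn.

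**Working it through.** **1. What a man withdrawn at the procedure still contributes.**

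| Item | Available? | Source |
|---|---|---|
| Baseline IPSS, QoL, Qmax, PVR | Yes | 6.1, 6.2 |
| Technical success | Yes: known failure, judged during the procedure | 7.2 |
| The complication itself | Yes: recorded whatever its suspected cause | 9.3 |
| Course of device-associated effects | Yes: followed until resolved or stable | 9.3 |
| Adverse-effect questioning at later visits | No | 9.3 |
| 3-month CT | No | 6.5 |
| 3-, 6- and 12-month IPSS, QoL, IIEF, Qmax, PVR | No | 6.5–6.7 |

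The loss falls mainly on efficacy.

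**2. The plan's own figure.** Section 8.1 states 3.60% precision for the percent change in IPSS with N = 20. It gives no SD and no confidence level, so the figure cannot be reproduced. If it is a 95% t half-width, the implied SD is 3.60 × √20 / 2.093 = 7.7 points. With 19 men and that SD the half-width is 3.71. Losing one man therefore barely changes precision; the issue is bias.

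**3. Shift in mean IPSS reduction.** Let completers average m percent, and let k withdrawn men have 0% improvement (both assumed). The mean over all 20 is m × (20 − k)/20, so the completer mean is too high by m × k/20.

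| m | k = 1: all-20 mean (excess) | k = 2: all-20 mean (excess) |
|---|---|---|
| 40 | 38.0 (2.0) | 36.0 (4.0) |
| 50 | 47.5 (2.5) | 45.0 (5.0) |
| 60 | 57.0 (3.0) | 54.0 (6.0) |

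**4. Clinical success.** Take 15 responders, in line with the 75% effectiveness quoted in 1.2 (a 2-year figure, used only for illustration). With all 20 as denominator, success is 15/20 = 75.0%. With one man dropped from the denominator it is 15/19 = 78.9%.

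**5. How many men.** Section 9.6 stops the study at more than one major complication, so one man is the usual case and about two the practical maximum.

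The chance of at least one major complication in 20 is 1 − (1 − p)^20:
- p = 0.003 (9.1): 5.8%. The chance of two or more is about 0.2%.
- p = 0.0109 (exact 95% upper limit for the 2 of 662 in 9.1): 19.6%.
- p = 0.05 (assumption): 64%.

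Each is an upper bound on the relevant event, because not every major complication stops a procedure. Section 1.5 says there are no published PAE data for this device, so its rate is unknown.

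**The case against.** The case against is substantial, and much of it stands.

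*Safety.* A reader might infer that the primary safety endpoint loses exactly the men it is about. The documents do not support that. The triggering complication is itself recorded, and 9.3 requires device-associated effects to be followed to resolution or stability, with no exception for withdrawn subjects. What can be missed is a later, separate event, or a finding on the 3-month CT.

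*Size.* A reader might infer that the bias exceeds the stated 3.60% precision. That needs two withdrawn men in a full cohort of 20. Given 9.6, this fits only if the second complication comes at or near the end of treatment, or if the scale in 9.6 (Society of Interventional Radiology) and the one in 3.4 (Clavien-Dindo) classify an event differently. If the second came early, the study would stop short of 20 and the 20-man precision would no longer be the yardstick. With one man the shift stays below 3.60.

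*Denominator.* A reader might infer that the plan commits to a completer analysis. It does not. The intent-to-treat wording and 8.3 point towards all subjects for the fractions; the defect is that no denominator is stated. A man who leaves after month 3 also keeps his 3-month data, so available-case is the accurate description.

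*Probability.* The documents' figures for other embolics are low: besides the 0.3%, 1.6.1 gives serious adverse events in 1% of 286 patients and 1.6.2 gives none in 38. The 5% rate above is only an assumption.

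*Second limb.* For men who cannot attend, rewording 4.6.1 recovers nothing; only an analysis rule helps.

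None of this restores the 6-month efficacy data of a man withdrawn under the first limb.

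**Conclusion.** The point holds for efficacy, at modest size. Followed as written, 4.6.1 and 4.6.2 produce outcome-related missing 6-month data that conflict with the intent-to-treat statement, and 8.2 and 8.3 have no rule for it. For the typical case of one man, the mean IPSS reduction is too high by 2.0–3.0 points, and clinical success reads 79% instead of 75% if completers are the denominator. These sizes assume 0% improvement in the withdrawn man, a completer mean of 40–60%, and 15 responders.

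At the cited 0.3% rate the chance that the situation arises at all is at most about 6%; for this device it is unknown. The effect on safety is partial, limited to later questioning and the 3-month CT. The plan should be corrected because the rule is unsound and the repair is simple, not because a large distortion is likely.

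**What to change.** 1. In 4.6.1, separate not completing the procedure from leaving the study. Any subject in whom PAE was started stays for the scheduled 3-, 6- and 12-month assessments, including the 3-month CT, unless he withdraws consent or cannot attend. This concerns data collection only; the clinical handling of the complication is left as it is.
2. In 8.2 and 8.3, name all subjects in whom PAE was started as the denominator for technical success, clinical success and complications. In 4.6.2, use the same starting point for replacement, since the text does not say whether an interrupted PAE counts as undergone.
3. Count a missing 6-month clinical success as non-success.
4. That rule does not cover the continuous primary endpoint. Report the mean IPSS change on available 6-month values, with a sensitivity analysis that sets a missing 6-month IPSS to no change from baseline.

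The cost is a few sentences of protocol text and, for the rare man affected, visits already in the schedule. The reported success rate and mean change may be slightly less favourable.

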4.6.2 Follow-up for Withdrawn Subjects

If a subject withdraws from the study, any recorded data will still be included in the analysis. Subjects will only be replaced if they withdrew prior to undergoing PAE.

5.0 Study Treatment or Diagnostic Product Procedures

5.1 Description

Subjects will be advised to stop taking their BPH medications two weeks prior to PAE. Though this is advised, it is not required if they cannot tolerate cessation. They will be given a dose of antibiotics on the day of the procedure and continue with oral antibiotics for seven days after the procedure. Additionally, non-steroidal anti-inflammatory medication will be administered mid-procedure. The patients will be given the choice of receiving intravenous anxiolytic and analgesic medication during procedure or proceeding with local anesthetic only.

Ultrasound-guided access into common femoral artery or radial artery will be obtained. An intra-arterial sheath will be placed. Through this sheath a diagnostic catheter will be used to perform pelvic angiography. Based on these images and CT angiography obtained before the procedure, a microcatheter will be fluoroscopically guided into the prostatic artery. LC Bead LUMI will then be injected under fluoroscopic guidance to prevent reflux and non-target embolization. Injection will continue until there is stasis. The catheter will then be guided into the contralateral prostatic artery and repeat embolization will be performed until stasis. If necessary, extraprostatic arterial anastomoses will be embolized with a coil or a gel-foam pledget to protect against non-target embolization. The catheter and sheath will then be removed and hemostasis will be achieved with compression or an intra-arterial closure device. The subject subsequently will be discharged home the same day or the following day.

It is anticipated that less than 4 milliliters of LC Bead LUMI will be required for bilateral embolization. LC Bead LUMI currently have FDA approval for embolization of hypervascular tumors and arterio-venous malformations.

5.2 Method for Assigning Subject to Treatment Groups

Because this is a pilot study to assess feasibility, all subjects will receive the study intervention (PAE).

5.3 Subject Compliance Monitoring

Study coordinators and physicians will inquire of the subjects to determine when they have stopped taking their BPH medications prior to the procedure. Additionally, the subjects will be asked if they completed all seven days of their post-procedural antibiotic regimen.

5.4 Prior and Concomitant Therapy

The subjects will be required to have been on medical therapy for BPH for at least six months prior to undergoing PAE. They will be advised to stop the BPH medications two weeks prior to undergoing PAE. They will be asked to discontinue BPH medication after PAE. Some patients may require maintenance of their BPH medications pending alternative therapy. Such medications include prescription and over-the-counter drugs. If potentially confounding medications are clinically appropriate to be taken concurrent with the study, dosage should not change during the study period unless medically necessary.

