7.2 Effectiveness Assessments

Technical success will be defined as bilateral prostatic artery embolization. This will be determined during the procedure. Clinical success will be defined by a reduction of IPSS of $\geq 25\%$ and reduction of QoL by ≥ 2 . The size of the prostate will be measured by CT at 3 the follow-up visit. IPSS, QoL, IIEF, PVR and Qmax will be measured at 3, 6 and 12-month follow-ups.

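### Clinical success in 7.2 sets no condition on later BPH procedures, so a man who improves only after one would count as a PAE success

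*Combined protocol and SAP*

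**What the plan says.** Section 5.4 deals with BPH drugs around the procedure. After PAE, "They will be asked to discontinue BPH medication after PAE". It then allows an exception: "Some patients may require maintenance of their BPH medications pending alternative therapy". For drugs that continue, "dosage should not change during the study period unless medically necessary". Nothing in 5.4 covers BPH procedures after PAE or gives any of these events a consequence in the analysis.

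The primary endpoint in 3.2 is "Reduction in IPSS at 6 months", with no condition on treatment in between. Section 7.2 reads "Clinical success will be defined by a reduction of IPSS of" at least 25%, together with a QoL fall of at least 2. It names no time point and does not require freedom from further BPH treatment.

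On who and what is analysed, 8.3 states "All subjects' data will be included for analysis even if follow up data is incomplete", and 4.6.1 states "Data will be included with an intent to treat analysis" without defining the term. Section 4.6.2 keeps whatever was recorded before a withdrawal. The investigator-led withdrawal rule concerns complications: "Subjects will be withdrawn from the study if a major complication occurs that prevents completion of PAE", or that prevents follow-up visits. Alternative BPH therapy is not a reason for withdrawal, so a retreated man stays in follow-up. Section 8.2 takes percent change from baseline to the final value, and visits run to 12 months. No endpoint in 3.2 to 3.5 counts retreatment, and the time and events table has no row for it.

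**The concern.** The study has one arm and is unblinded, so no comparison group would show that an improvement came from something other than the embolization. Suppose PAE helps a man too little, he has another BPH procedure before month 6, and he then attends the visit with better IPSS and QoL scores. Under 7.2 he is a clinical success, although from the point of view of PAE with this bead he is one of the clearer failures.

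The stated purpose (2.0, 8.1) is to estimate endpoint distributions and to supply planning figures for a larger trial. A success rate that includes men improved by another procedure would be read as the success rate of PAE. A larger trial planned on it could be too small.

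**Working it through.** **The plan's own figure.** Section 8.1 gives 3.60% precision for the percent change in IPSS at 6 months with n = 20. No SD is given, so the figure can only be solved backwards.

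- Read as a 95% half-width: SD = 3.60 × √20 / 1.96 = 8.2 points (normal), or 3.60 × √20 / 2.093 = 7.7 points (t, 19 df).
- Read as a standard error: SD = 3.60 × √20 = 16.1 points.

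The figure cannot be reproduced. It is also a poor yardstick here. If 19 men fall by 70% and one by 10% (assumed values), the SD is 60/√20 = 13.4 points and the 95% half-width is 2.093 × 13.4/√20 = 6.3 points, well above 3.60. The shifts below are therefore given in their own units.

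**Inputs.** n = 20 treated men (4.2 and 8.1; 4.6.2 replaces only men who withdraw before PAE). k is the number of men whose month-6 scores follow a later BPH procedure. d is the extra IPSS improvement that the procedure brings, in percentage points of baseline. The documents give neither k nor d, so both are assumed.

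**Clinical success.** A man who meets both criteria only because of a later procedure adds 1/20 = 5 percentage points. An illustration with assumed counts and exact 95% intervals:

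| Successes | Rate | 95% CI |
|---|---|---|
| 15/20 as scored under 7.2 | 75% | 51 to 91% |
| 14/20 if one is reclassified | 70% | 46 to 88% |
| 12/20 if three are reclassified | 60% | 36 to 81% |

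QoL must also fall by 2 or more, so a better IPSS alone does not make a success. Effective later therapy could move both scores.

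**Mean percent change in IPSS.** Shift = k × d/20.

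| Assumed d | k = 1 | k = 2 | k = 3 |
|---|---|---|---|
| 25 | 1.25 | 2.5 | 3.75 |
| 50 | 2.5 | 5.0 | 7.5 |
| 60 | 3.0 | 6.0 | 9.0 |

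**The case against.** The strongest reply is that keeping every score, whatever happened after PAE, is a legitimate approach. Sections 8.3 and 4.6 can be read that way, and a later trial might want the same quantity. That stands for the IPSS change. The as-observed mean is a sound estimate of PAE followed by usual care and needs only to be labelled as such. Making baseline-imputed scores the main estimate would be a debatable choice, would discard real partial benefit, and would alter the SD the pilot is meant to supply. The reply is weaker for clinical success, whose name and definition credit the outcome to PAE.

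It is also fair that 5.4 is a paragraph about drugs. It says some men may be waiting for other therapy. It does not say what therapy, how many men, or that they receive it before day 180. Surgery and repeat embolization are possible examples, not the protocol's words. That later scores are pooled is inferred from the all-data rule and the absence of any exception; no sentence says it outright.

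Some capture exists already: 9.3 has adverse effects asked about at each follow-up visit. The CRF is not among the documents, so whether it has a field for later procedures cannot be checked.

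A reader might infer two stronger points that the documents do not support:

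- **Catheterized men vanish from the means.** Nothing says such a man has no valid IPSS, which is a questionnaire, or that he is dropped.
- **The documents show how many men will be affected.** The 7.9% in 9.1 is acute retention, listed among minor complications; it is not catheter dependence at month 6. The 75% in 1.2 is effectiveness at 2 years. Neither is a 6-month retreatment rate, and no such rate is given.

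**Conclusion.** The point holds for the definition of clinical success. Under 7.2, 8.3 and 4.6 as written, a man who meets both score criteria only after a later BPH procedure is a PAE success, at 5 percentage points per man. This follows from the text and from n = 20, and needs no assumption about effect size. How many men it would touch is unknown.

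For the mean IPSS change, the effect is k × d/20, or 1.25 to 3.0 points per man if d lies between 25 and 60. That range is assumed. Here the gap is one of labelling and reporting, since including all data is defensible.

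A reader might take this as a flaw that invalidates the study. It does not. The pilot is descriptive and has no hypothesis test or success threshold, and clinical success is not among the endpoints listed in 3.2 and 3.3. It should be fixed because the remedy is cheap and the figures feed the next trial.

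**What to change.** - **7.2:** define clinical success at month 6 as both score criteria met with no surgical or interventional BPH therapy between PAE and that visit. Count men who had such therapy as failures, with all treated men in the denominator.
- **8.2 and 8.3:** keep the as-observed 6-month IPSS change and state that it includes the effect of any later therapy. Report beside it the number of men retreated and a sensitivity analysis that does not credit post-therapy scores to PAE. One option is to use each such man's last IPSS before the later procedure.
- **Data collection:** record the date and type of any later BPH procedure at each visit, if the CRF does not already do so, and add a row to the time and events table.

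The cost is a few sentences and at most one CRF line; patient care does not change. The reported success rate may be slightly lower, and a man who had already met both criteria before a later procedure would also count as a failure.
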